5. High Risk with Explanation Based on Algorithm - message(s) disclosing the patient's *high-risk status* with the added explanation that they are at high risk based on a *computer algorithm review of their medical records* and with the top *reason(s) why they are considered high risk*

Patients in groups 4 and 5 were further randomized to receive one reason or three reasons why they were at high risk (per the medical record review or the algorithm). Randomization occurred separately within each risk and message group. For example, in group 5 (algorithm) half of patients in the top 3% of risk received messages including one reason, while the other half received messages with three reasons.

Message modalities

Patients randomized to groups 2-5 were sent messages in up to 3 modalities: 1. a letter, 2. a myGeisinger (myChart patient portal) message, and 3. an SMS (text) message. Patients with a valid address on file were sent a letter. Patients were sent a myGeisinger message and/or an SMS if they were eligible and if their letter was not returned to sender.

Project status

All intervention messages have been sent. Data collection is ongoing. The study team has not yet extracted or analyzed any outcome data from the study.

Planned Analyses

Primary Outcome

Flu vaccination at 2 weeks after the final outreach date [Time Frame: Within 2 weeks of the final outreach date, 8 weeks + 1 day after the study start] *

Question 1: Does informing patients that they are at high risk for flu and flu-related complications increase the likelihood that they will get vaccinated?

Analysis 1a (Confirmatory): We will test the hypothesis that patients who were sent messages with information about their risk status (patients randomized to message group 3, 4, or 5) will exhibit improved flu vaccination rates compared with patients who were sent messages without risk information (group 2).

Analysis 1b (Confirmatory): We will test the hypothesis that patients who were sent messages with information about their risk status (those in group 3, 4, or 5) will exhibit improved flu vaccination rates compared with patients assigned to the no-contact control group (group 1).

For analyses 1a and 1b, we will run OLS regressions. For both regressions, we will include a binary predictor variable coding separately for baseline (group 2 for analysis 1a and group 1 for analysis 1b), and message (all patients in groups 3-5).

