Some patients lived at the same address, but we decided to randomize patients independently, without accounting for whether a household member was also in the study. Therefore, some patients may have been assigned to different groups from their household members. Alternatively, it is possible household members were assigned to the same group. Either possibility may affect the impact of our intervention (e.g., the same messages received by multiple household members may reinforce the message and strengthen the impact of the messages, while different messages could cause confusion and weaken the messages' effectiveness). To ensure findings do not depend on such interactions between patients residing at the same address, we will run a sensitivity analysis by removing all patients who share an address with another patient in the study and computing the same analyses listed above.

Recent work suggests that OLS regressions are appropriate in randomized experiments with binary outcome variables such as ours (Gomilla, 2021). However, as a robustness check, we will also run the regressions described above as logistic regressions instead of OLS regressions.

Additionally, we plan to exclude some patients from our primary analyses, as noted below in "Analysis exclusion criteria." We will run an intent-to-treat analysis as a robustness check, including all patients who passed away during our study, those who were inadvertently sent protective risk reasons, and those who were vaccinated prior to the study beginning. We will however exclude from all analyses all patients who passed away prior to our study start date (9/9/21), and those inadvertently included despite not satisfying all of the inclusion criteria. A small group of patients did not have a valid mailing address in their medical records, or their print letters were returned to sender. Our subsequent myGeisinger messages referred patients to the letter that was sent. To avoid confusion, we did not send myGeisinger or SMS messages to patients who were never sent a letter, or whose mail was returned prior to these modality send dates. We do not exclude these patients because this would differentially exclude subjects

across the arms. We will note the small fraction of the treatment arms that were not treated for this reason.

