We will also rerun the OLS regression analyses including a binary covariate for whether each patient has an assigned Primary Care Provider (PCP) who works at Geisinger, as flu shot data in the Geisinger EHR may be less reliable from those with an external PCP.

Finally, as an additional robustness check, we will run OLS regression analyses controlling for sex, 10-year age bins, and interactions among sex and age as covariates.

Secondary outcomes

We will use the approaches described in analyses 1-4 above to evaluate the impact of the intervention on the secondary outcome measures listed in the pre-registration:

1. Flu vaccination at 9 weeks after the final outreach date [Time Frame: Within 9 weeks of the final outreach date, within 15 weeks + 1 day of the study start] *

Received a flu vaccination

2. Flu diagnosis [Time Frame: 8 months (between September 9, 2021 and April 30, 2022)]

Received a "high confidence flu" diagnosis (with positive polymerase chain reaction [PCR]/antigen/molecular test) and/or "likely flu" diagnosis (as assessed via International Classification of Disease [ICD] codes or Tamiflu administration or positive PCR/antigen/molecular test)

3. Flu complications [Time Frame: 11 months (between September 9, 2021 and July 31, 2022)]

Diagnosed with flu-related complications

4. Healthcare utilization [Time Frame: 11 months (between September 9, 2021 and July 31, 2022)]

Visited ER, was hospitalized, or had flu-related insurance claims

*Because our outreach timeline was delayed (see above), we will delay the time frame for Secondary Outcome 1 from 3 months following the study start to 9 weeks following the final outreach date.

Additional exploratory analyses

1. Number of reasons

Patients in groups 4 and 5 were randomized to receive either 1 or 3 of the top reasons why they were considered high risk for flu. We will run an OLS regression testing for main effects and interactions between the number of reasons (1 reason, 3 reasons) and message type (group 4: medical records message, group 5: algorithm message) on flu vaccination.

2. Age

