Contraindicated patients: We unintentionally failed to remove a small number of patients contraindicated for flu vaccines from the sample prior to sending letters. After the error was discovered (after letters were sent, but prior to myGeisinger or SMS messages), because this was an exclusion criterion for the study, we removed the patients completely from the study, including from all analyses.

Patients deceased prior to our study start date (9/9/21): Midway through the study, we received an updated list of patients who were deceased. Some had died prior to the study beginning but medical records had not yet been updated to reflect the date of death. These patients will be removed from all analyses.

The following groups of patients will be excluded from all analyses, except the intent-to-treat analysis (robustness analysis) as described above:

Patients deceased during the study: A very small number of patients were recorded as deceased between the date we originally pulled the data and the date of the updated pull. These patients will be removed from analyses.

Patients sent protective risk reasons: Additionally, in determining the reasons each person was considered high risk, we unintentionally included reasons that were negatively weighted for a small number of patients. That is, for these patients, one or two of the reasons listed for their high-risk determination were *protective* against flu, despite their overall high-risk designation by the model. These patients will be removed because their messages may have been confusing and were not the precise messages we originally intended to send. For consistency across groups, we will also remove those in groups who were not sent reasons, but who would have received protective risk reasons had reasons been included in their messages.

Patients vaccinated prior to the study beginning: Area pharmacies and some Geisinger clinics began offering flu vaccines prior to our study beginning. We will remove patients from analysis who received a flu shot prior to 9/9/21, the study start date.

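### As worded, the protective-reason exclusion can follow the one-or-three-reasons randomisation and bias that exploratory comparison

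*SAP*

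**What the plan says.** Under Sample and Randomization, the SAP sub-randomises groups 4 and 5 to one or three reasons. Its example for group 5 is that "half of patients in the top 3% of risk received messages including one reason, while the other half received messages with three reasons". Groups 1-3 have no such assignment. Additional exploratory analyses, item 1, uses this factor: "We will run an OLS regression testing for main effects and interactions between the number of reasons" and message type.

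Analysis exclusion criteria then describes an error: "in determining the reasons each person was considered high risk, we unintentionally included reasons that were negatively weighted for a small number of patients". For these patients, "one or two of the reasons listed for their high-risk determination were" protective. The reason given for dropping them is the message itself: "These patients will be removed because their messages may have been confusing and were not the precise messages we originally intended to send". The rule is extended to other arms as follows: "For consistency across groups, we will also remove those in groups who were not sent reasons, but who would have received protective risk reasons". Its scope is wide: "The following groups of patients will be excluded from all analyses, except the intent-to-treat analysis". Sensitivity analyses and robustness checks describes the patients restored in that analysis as "those who were inadvertently sent protective risk reasons".

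The SAP gives no count of these patients beyond calling them few, and no breakdown by group or by number of reasons.

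**The concern.** The category is defined by what was sent and listed, and is justified by the content of the message. In groups 4 and 5 that content was itself randomised. A patient with a true risk factor at rank 1 and a protective factor only at rank 2 or 3 is removed under three reasons and retained under one. The consistency sentence does not repair this. It reaches only groups that were sent no reasons, and one-reason patients were sent a reason.

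A second gap concerns groups 1-3. They had no one-or-three assignment, so the SAP leaves open whether a patient there is screened on the top reason, on the top three, or on a matching split.

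At stake is the randomised one-versus-three comparison, whose analysis set would be selected after randomisation by the factor under test. Analyses 1a, 1b and 2, and the group 3 contrasts of Analysis 4, could carry a smaller bias, but only if groups 1-3 are screened on a fixed list length while groups 4 and 5 are screened on what was displayed. On any reading, Analysis 3 and group 4 versus group 5 are unaffected.

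**Working it through.** **Inputs from the SAP.** Baseline rate 40%; 9,400 per group planned; 45,164 patients in total, so 45,164/5 = 9,033 per group if equal. One versus three reasons, pooled over groups 4 and 5, also has about 9,033 per level.

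**Assumptions, not in the documents.** Two-sided 5% level. q = share of patients protective only at ranks 2-3, taken as 0.5%, 1% and 2%. g = gap in vaccination rate between these patients and the rest, taken as 5 to 30 points. p = share whose top reason is protective (removed in every cell), taken as 0; p = 1% barely matters (at q = 1%, g = 10 the bias is 0.101 instead of 0.100 points).

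**The SAP's own power figure.** For 40% vs 42% with 9,400 per group: [0.02 - 1.960 × √(2 × 0.41 × 0.59/9,400)] / √((0.24 + 0.2436)/9,400) = (0.02 - 0.01406)/0.00717 = 0.83, so power is 79.6%. The stated 80% reproduces. At 9,033 per group it is 78.0%.

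**Does the critical kind of patient exist?** The SAP reports one or two protective reasons per affected patient. A list with two must have at least one below rank 1, so protective factors do occur at ranks 2-3. How many patients have them only there is not stated.

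**Bias under the literal rule, with no true effect.**
- One-reason mean: (1 - q) × 40% + q × (40% + g) = 40% + q·g. Three-reason mean: 40%. Size of the bias: q × g.
- Groups 4 and 5 pooled have a mean of about 40% + q·g/2. If group 3 is screened on three reasons, the Analysis 2 bias is about q × g/2.
- Groups 3-5 pooled against group 2 or group 1, screened the same way: about q × g/3.
- If groups 1-3 are screened on one reason, the last two keep their size and change sign. With the same one-or-three split they are zero.
- The number-by-message interaction has no bias, because the selection is the same in groups 4 and 5.

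**Standard errors at 40%.**
- One vs three: √(0.24 × 2/9,033) = 0.729 points.
- Analysis 2: √(0.24 × (1/9,033 + 1/18,066)) = 0.631 points.
- Analyses 1a and 1b: √(0.24 × (1/9,033 + 1/27,098)) = 0.595 points.
- 80%-power difference for one vs three: (1.960 + 0.842) × 0.729 = 2.04 points.

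**Results.** Type I error is from a two-sided normal test with its mean shifted by bias/SE.

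| q | One vs three: bias in points (type I error), g = 5 to 30 | Analysis 2, groups 1-3 screened on three | 1a/1b, same screening |
|---|---|---|---|
| 0.5% | 0.025-0.15 (5.0-5.5%) | 0.013-0.075 (at most 5.2%) | 0.008-0.05 (at most 5.1%) |
| 1% | 0.05-0.30 (5.05-7.0%) | 0.025-0.15 (at most 5.7%) | 0.02-0.10 (at most 5.3%) |
| 2% | 0.10-0.60 (5.2-13%) | 0.05-0.30 (at most 7.7%) | 0.03-0.20 (at most 6.3%) |

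**Break-even.** For one vs three, type I error reaches 6% at a bias of 0.215 points. That needs a gap of 0.215/q: about 43 points at q = 0.5%, 21 at 1% and 11 at 2%. For Analysis 2 it is reached at 0.186 points, a gap of 0.186/(q/2): about 37 points at q = 1% and 19 at 2%.

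**One list for everyone.** If every patient is screened on the same list whatever was displayed, the removed share is equal in expectation in all cells and the bias is zero for every q and g.

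**The case against.** The literal reading is not the only one. The SAP places the error at the step where each person's reasons were determined, which is a patient-level step. Extending the exclusion to groups 1-3 requires a stored reason list for patients who received none. The stated aim is consistency, and elsewhere the SAP keeps patients with undelivered letters because dropping them would be unequal across arms. A single list screened for everyone fits all of this and gives no bias.

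The fully exposed contrast is exploratory, the excluded set is described as small, and at a 10-point gap with q = 1% type I error is only 5.2%. The 13% figure needs q = 2% and a 30-point gap together, and nothing in the documents supports a gap that large. Bias in Analyses 1a, 1b and 2 needs a hybrid rule that would defeat the consistency sentence. The pre-specified intent-to-treat analysis restores these patients and is free of this bias.

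All of this is accurate, and it limits the size of the problem. It does not remove it. The words for what was sent, what was listed and what the message said point to displayed reasons, and an analyst following them would exclude differentially. The intent-to-treat check is introduced against the primary analyses, and the SAP does not say that it is run for the number-of-reasons model.

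**Conclusion.** The concern holds. Followed as worded, the exclusion selects the number-of-reasons analysis set on the randomised factor, and the consistency sentence does not reach the cells where this happens. The bias can arise only if some patients are protective solely at ranks 2-3 and vaccinate at a different rate from the rest; the documents establish neither. For q up to 1% and gaps up to 30 points the bias is at most 0.30 points, under half a standard error, with type I error at most 7.0%. At q = 2% and the widest gap it is 0.60 points and 13%. Effects on the confirmatory analyses are smaller and conditional on fixed-length screening of groups 1-3. This should be fixed because it is cheap and can still be settled blind; it does not threaten the main conclusions.

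**What to change.** Before outcomes are extracted, state in Analysis exclusion criteria that the exclusion is one flag computed from the pre-messaging model output: any negatively weighted factor among the patient's top three. Apply it identically in all five groups and both reason-count cells, whether or not the factor was displayed. Report the number removed by group and by reason count. If one list is already being screened for everyone, the SAP only needs to say so.

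The cost is one or two sentences and one flag. Project status says no outcome data have been extracted or analysed, so the choice can still be made without knowledge of results. The downside is that some one-reason patients whose messages were correct are also dropped: q × 9,033, or about 45, 90 or 181 at q = 0.5%, 1% or 2%. Power for 40% vs 42% between two groups falls from 78.0% to 77.8%, 77.6% or 77.2% if 0.5%, 1% or 2% of the sample is removed.
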